2.2 Secondary objectives and endpoints

• To determine the objective response rate (ORR) by RECIST 1.1 criteria

- To determine the Clinical Benefit Rate (CR + PR + SD)
- To determine the time to progression (TTP)
- To determine overall survival (OS)
- To determine the safety profile and tolerability in this population
- To determine compliance with intended treatment (% of completion of the treatment)

3. SELECTION OF SUBJECTS

3.1 Number of Subjects

A total of 33 patients with metastatic or locally advanced unresectable pancreatic adenocarcinoma after progression through first line chemotherapy.

3.2 Inclusion Criteria

Subjects must meet all of the following criteria to be eligible for study participation:

- Clinical diagnosis of confirmed of adenocarcinoma of the pancreas, with pathologic confirmation of adenocarcinoma.
- Subjects must have measurable disease per RECIST 1.1 criteria.
- Metastatic or locally advanced unresectable disease. Subjects without clear evidence of distant metastatic disease will be presented at multidisciplinary tumor board for discussion of disease resectability.
- Refractory or intolerant to 1 or 2 prior regimens of standard chemotherapy for metastatic or locally advanced pancreatic cancer.
 a. Patients who have progressed based on imaging during or within 3 months of the last administration of each standard chemotherapy, or
- b. Patients who have withdrawn from standard treatment due to unacceptable toxicity warranting discontinuation of treatment and precluding retreatment with the same agent prior to progression of disease will also be eligible to enter the study.TAS102 will be planned to start after disease progression on first- or second-line chemotherapy, provided any prior chemotherapy-related toxicities have resolved to less than or equal to Grade 1 or baseline within 28 days of the date the subject signs the informed consent form. Grade 2 or greater toxicities including alopecia, skin pigmentation, and platinum induced neurotoxicity/neuropathy are acceptable for starting on trial, as these toxicities do not preclude treatment with TAS-102
- ECOG Performance Status of 0-2
- Capacity to understand and sign the informed consent document
- Able to take medications orally
- Life expectancy \geq 12 weeks as predicted by the treating oncologist's clinician judgement
- Age ≥ 18 years
- Subjects on anticoagulation need to have no evidence of uncontrolled bleeding and be on a stable anticoagulation dose for at least 2 weeks prior to the date the subject starts study drug.
- Women of childbearing potential (WOCBP) must be using an adequate method of contraception to avoid pregnancy throughout the study and for at least 6 months after the last dose of study drug to minimize the risk of pregnancy. Prior to signing the informed consent

form, women of childbearing potential must be advised of the importance of avoiding pregnancy during trial participation and the potential risk factors for an unintentional pregnancy.

- WOCBP include any woman who has experienced menarche and who has not undergone successful surgical sterilization (hysterectomy, bilateral tubal ligation, or bilateral oophorectomy) or who is not post-menopausal. Post-menopause is defined as:
 - Amenorrhea that has lasted for ≥ 12 consecutive months without another cause, or
 - For women with irregular menstrual periods who are taking hormone replacement therapy (HRT), a documented serum follicle-stimulating hormone (FSH) level of greater than 35 mIU/mL.
- Males with female partners of child-bearing potential must agree to use physician-approved contraceptive methods (*e.g.*, abstinence, condoms, vasectomy) throughout the study and should avoid conceiving children for 3 months following the last dose of study drug.
- Baseline laboratory values (bone marrow, renal, hepatic) must include:
 - Adequate bone marrow function:
 - Absolute neutrophil count $\geq 1500/$ mm³
 - Platelet count $\geq 75,000/$ mm³
 - HGB equal to or greater than 7g/dL
 - Renal function:
 - Serum creatinine ≤ 1.5 mg
 - Hepatic function:
 - Total bilirubin $\leq 1.5 \text{ mg/dL}$
 - AST and ALT equal to or less than 3 times the upper limit of normal for patients without hepatic involvement, or AST and ALT equal to or less than 5 times the upper limit of normal for patients with hepatic involvement
 - Serum calcium $\leq 12 \text{ mg/dl}$

3.3 Exclusion Criteria

Subjects with any of the following will not be eligible for study participation:

- Pregnant or lactating females
- Previously taken TAS-102
- Myocardial infarction or ischemia within the 6 months before first dose of study drug
- Uncontrolled, clinically significant dysrhythmia
- Intervention for ascites or pleural effusions within 4 weeks before first dose of study drug
- Previous surgery and/or radiotherapy may have been performed 2 or more weeks prior to the date the subject starts study treatment, provided that it was to a non-target lesion and there is still evidence of target lesion disease progression radiographically or intolerance to first- or second-line chemotherapy.
- Major surgery within 4 weeks before first dose of study drug (the surgical incision should be fully healed prior to drug administration).
- Any anticancer therapy within 3 weeks before first dose of study drug (with the exception of bevacizumab, which must not have been taken within 4 weeks before first dose of study drug).

- Extended field radiation within 4 weeks before first dose of study drug or limited field radiation within 2 weeks before first dose of study drug.
- Any investigational agent received within prior 4 weeks before first dose of study drug Subjects must not have more than one active malignancy at the time of enrollment (Patients with a prior or concurrent malignancy whose natural history or treatment does not have the potential to interfere with the safety or efficacy assessment of the investigational regimen [as determined by the treatment physician and approved by the PI] may be included).
- Has unresolved toxicity of greater than or equal to Common Terminology Criteria for Adverse Events (CTCAE) Grade 2 attributed to any prior therapies (excluding anemia, alopecia, skin pigmentation, and platinum-induced neurotoxicity).
- Any co-morbid condition that, in the view of the attending physician, renders the subject at high risk from treatment complications including but not limited to chronic infections, uncontrolled diabetes, congestive heart failure according to the NYHA criteria, untreated brain metastases, liver or renal failure, gastrointestinal hemorrhage.
- History of any other disease, metabolic dysfunction, physical examination finding, or clinical laboratory finding giving reasonable suspicion of a disease or condition that contraindicates the use of protocol therapy or that might affect the interpretation of the results of the study or that puts the subject at high risk for treatment complications, in the opinion of the treating physician.
- Known untreated or unstable brain metastases or leptomeningeal disease
- Active infection
- Prisoners or subjects who are involuntarily incarcerated or subjects who are compulsorily detained for treatment of either a psychiatric or physical illness.
- Subjects demonstrating an inability to comply with the study and/or follow-up procedures.

3.4 Inclusion of Women and Minorities

Both men and women of all races and ethnic groups will be eligible for this trial. Men and women will be recruited with no preference to gender. No exclusion to this study will be based on race. Minorities will be actively recruited to participate. Only adults (age ≥ 18 years of age) capable of providing their own consent will be eligible.

4. REGISTRATION PROCEDURES

All consented subjects must be entered into the University of Florida's Clinical Trial Management System (OnCore) prior to assignment of a subject identification number. The study team must submit the completed study specific eligibility checklist, supporting source documentation and a copy of the signed informed consent document(s) to the UFHCC Project Management Office (PMO: [contact]) or their assigned Project Manager. Unsigned eligibility checklists or eligibility packets with missing or incomplete information may be returned to the study team. Upon receipt of a completed eligibility packet, the designated Project Manager will review the source to verify eligibility and assign a subject number. If eligibility cannot be confirmed, the project manager will query the site for clarification or additional documents as needed. Subjects failing to meet all study eligibility requirements will not be able to participate in the trial. Subjects who are not initiated on study drug, but sign informed consent and undergo at least some of the screening procedures will be considered screening failures. A record of these subjects will be maintained by the study site.

5. STUDY TREATMENT

All subjects entering the screening phase will receive a unique subject number. This number will be used to identify the subject throughout the study. Subjects withdrawn from the study will retain their subject number.

5.1 Treatment Schedule/Administration:

Treatment must begin within 28 days of the date the subject is entered into the CTMS (OnCore). Upon confirmation of eligibility and provision of subject study number, subjects will receive TAS-102 at the following dose and schedule. The number of tablets of each strength that are needed for the 35 mg/m² dose per BSA level is shown in Table 1.

| TAS-102 | BSA ^a | Dosage in | Total daily | Tablets per dose | |
|----------------------|-------------------|------------|-------------|------------------|-------|
| Dose | (m ²) | mg | dose (mg) | _ | |
| (2x daily) | | (2x daily) | | 15 mg | 20 mg |
| 35 mg/m ² | < 1.07 | 35 | 70 | 1 | 1 |
| | 1.07 - 1.22 | 40 | 80 | 0 | 2 |
| | 1.23 - 1.37 | 45 | 90 | 3 | 0 |
| | 1.38 - 1.52 | 50 | 100 | 2 | 1 |
| | 1.53 - 1.68 | 55 | 110 | 1 | 2 |
| | 1.69 - 1.83 | 60 | 120 | 0 | 3 |
| | 1.84 - 1.98 | 65 | 130 | 3 | 1 |
| | 1.99 - 2.14 | 70 | 140 | 2 | 2 |
| | 2.15 - 2.29 | 75 | 150 | 1 | 3 |
| | ≥2.30 | 80 | 160 | 0 | 4 |
| | | | | | |

 Table 1. Dose Calculations Based off BSA

a Calculate body surface area (BSA) to 2 decimal places.

Each treatment cycle will be 28 days in duration. One treatment cycle consists of the following:

Days 1 through 5: TAS-102 ($35 \text{ mg/m}^2/\text{dose}$) orally 2 times daily with the first dose administered in the morning of Day 1 of each cycle and the last dose administered in the evening of Day 5.

Days 6 through 7: Rest

Days 8 through 12: TAS-102 (35 mg/m²/dose) orally 2 times daily with the first dose administered in the morning of Day 8 of each cycle and the last dose administered in the evening of Day 12.

Days 13 through 28: Rest

The patient must be instructed in the handling of study medication as follows:

- To store the study medication at room temperature
- To only remove from the study medication kit the amount of tablets needed at the time of dosing
- Not to remove doses in advance of the next scheduled dosing
- To make every effort to take doses on schedule
- To take study medication within 1 hour after completing a meal (morning and evening meals) with a glass of water per the dose schedule
- If the patient vomits after taking study medication, the patient should not take another dose.
- To keep study medication in a safe place and out of reach of children

To bring all used and unused study medication kits to the site at each visit Any missed doses reported by the subject should be recorded in the subject's source documents. Subjects should not take additional doses to make up for missed or held doses.

Complete blood count (CBC) with differential will be checked on the first day of each cycle, every 28 days, or within 72 hours of each cycle upon completion of Cycle 1 to accommodate subjects with long travel distance and on Day 15 of each cycle to monitor for development of anemia and neutropenia. In the absence of significant treatment-related abnormalities, and documentation of an ANC greater than or equal to 1500/ mm³ and platelet count of greater than or equal to 75,000/ mm³ treatment cycles will continue every 28 days until subject intolerance, subject discontinuation, or disease progression. Tumor status will be assessed every two cycles.

5.2 Dose Calculations

Refer to 'Table 1. Dose Calculation Table Based off BSA" in Section 5.1.

5.3 Concomitant Therapy

Use of anti-neoplastic or anti-tumor therapies not part of the study treatment, including surgery, chemotherapy, radiation therapy, immunotherapy, and hormonal anticancer therapy, is not permitted while participating in this study. Use of erythropoietin stimulating agents is also not permitted. Use of concurrent investigational agents is not permitted.

Relevant medical history should be obtained at screening and include prior medications and treatment history. All medications taken within 3 weeks prior to screening, regardless of indication, should be recorded

Any therapy or medication (except study drugs), administered from first dose of study drug until 30 days after the last dose of either study drug, is considered a concomitant therapy or medication. However, if another course of anticancer therapy is initiated prior to the 30-day follow-up period visit, a record of concomitant medications will no longer be performed. If the use of any concomitant treatments (medications or procedures) becomes necessary, the treatment must be recorded, including the name of the drug or treatment, dose, route, date, indication for use, expected duration, and frequency of treatment. Assessment and documentation of concomitant medications will be done at each visit.

5.3.1 Allowed Concomitant Therapy

Subjects may continue on their chronic medications. Subjects on anticoagulation need to have no evidence of bleeding and be on a stable anticoagulation dose for at least 2 weeks prior to first dose of study drug.

Use of granulocyte colony stimulating factor and packed red cell transfusions are permitted to maintain adequate bone marrow function according to institutional standards. If no standards are in place for the use of growth factors, then follow the 2015 ASCO Clinical Practice Guidelines for use of WBC growth factors

5.3.2 Prohibited Concomitant Therapy

Subjects are prohibited from receiving the following therapies during the Screening and Treatment Phase of this trial:

- Antineoplastic systemic chemotherapy or biological therapy
- Immunotherapy not specified in this protocol
- Hormonal anticancer therapy not specified in this protocol
- Chemotherapy not specified in this protocol
- Investigational agents other than the study drug in this trial
- Live vaccines within 30 days prior to the first dose of trial treatment and while participating in the trial. Examples of live vaccines include, but are not limited to, the following: measles, mumps, rubella, chicken pox, yellow fever, rabies, BCG, and typhoid (oral) vaccine. Seasonal influenza vaccines for injection are generally killed virus vaccines and are allowed. However, intranasal influenza vaccines (e.g. Flu Mist®) are live attenuated vaccines, and are not allowed

- Erythropoietin stimulating agents
- Radiation therapy
- Cancer-related surgery

NOTE: Radiation therapy to a symptomatic solitary lesion may be considered on an exceptional case by case basis after consultation with sponsor-investigator. The subject must have clear measurable disease outside the radiated field. Administration of strictly palliative radiation therapy to a single symptomatic lesion will not be considered clinical progression for the purposes of determining PFS.

5.4 Dose Modifications

Doses will be reduced or modified if AEs are observed according to the criteria described below.

The National Cancer Institute (NCI) Common Toxicity Criteria for Adverse Events Version 4.0.3 (CTCAE) will be used to grade adverse event toxicity (http://evs.nci.nih.gov/ftp1/CTCAE/About.html).

5.4.1 Dose Modification Explained

Subjects are permitted dose reduction(s) to a minimum dose of 20 mg/m^2 (40 mg/m^2 /day) in 5 mg/m² (10 mg/m^2 /day) steps. A maximum of three dose reductions in decrements of 5 mg per square meter are allowed for toxicity to a minimum dose of 20 mg/m^2 . Do not escalate dose once it has been reduced. Refer to Table 2 located in this sub-section.

Table 2: TAS-102 Dose Modification Table

| tot at white | 1 | Dosage in | An and a second | Tablets | per dose | Cards I | oer Cycle |
|----------------------------|--------------------------|-----------------------------|--------------------------|---------------------|---------------------|---------|-----------|
| TAS-102 Dose (2x daily) | BSA (m ²) | mg (2x daily) | Total daily dose (mg) | 15 mg | 20 mg | 15 mg | 20 mg |
| Level 1 Dose Red | uction: From 3 | 5 mg/m ² to 30 | mg/m ² | | | | |
| 30 mg/m^2 | < 1.09 | 30 | 60 | 2 | 0 | 2 | 0 |
| | 1.09 - 1.24 | 35 | 70 | 1 | 1 | 1 | 1 |
| | 1.25 - 1.39 | 40 | 80 | 0 | 2 | 0 | 2 |
| | 1.40 - 1.54 | 45 | 90 | 3 | 0 | 3 | 0 |
| | 1.55 - 1.69 | 50 | 100 | 2 | 1 | 2 | 1 |
| | 1.70 - 1.94 | 55 | 110 | 1 | 2 | 1 | 2 |
| | 1.95 - 2.09 | 60 | 120 | 0 | 3 | 0 | 3 |
| | 2.10 - 2.28 | 65 | 130 | 3 | 1 | 3 | 1 |
| | ≥ 2.29 | 70 | 140 | 2 | 2 | 2 | 2 |
| Level 2 Dose Redu | ection: From 30 | 0 mg/m ² to 25 | mg/m ² | | | | |
| 25 mg/m^2 | < 1.10 | 25 ^a | 50 ^a | 2 (PM) ^a | 1 (AM) ^a | 2 | 1 |
| | 1.10 - 1.29 | 30 | 60 | 2 | 0 | 2 | 0 |
| | 1.30 - 1.49 | 35 | 70 | 1 | 1 | 1 | 1 |
| | 1.50 - 1.69 | 40 | 80 | 0 | 2 | 0 | 2 |
| | 1.70 - 1.89 | 45 | 90 | 3 | 0 | 3 | 0 |
| | 1.90 - 2.09 | 50 | 100 | 2 | 1 | 2 | 1 |
| | 2.10 - 2.29 | 55 | 110 | 1 | 2 | 1 | 2 |
| | \geq 2.30 | 60 | 120 | 0 | 3 | 0 | 3 |
| Level 3 Dose Redu | iction: From 25 | 5 mg/m ² to 20 i | mg/m ² | | | | |
| 20 mg/m^2 | < 1.14 | 20 | 40 | 0 | 1 | 0 | 1 |
| | 1.14 - 1.34 | 25 ^a | 50 ^a | 2 (PM) ^a | 1 (AM) ^a | 2 | 1 |
| | 1.35 - 1.59 | 30 | 60 | 2 | 0 | 2 | 0 |
| | 1.60 - 1.94 | 35 | 70 | 1 | 1 | 1 | 1 |
| | 1.95 - 2.09 | 40 | 80 | 0 | 2 | 0 | 2 |
| | 2.10 - 2.34 | 45 | 90 | 3 | 0 | 3 | 0 |
| | ≥ 2.35 | 50 | 100 | 2 | 1 | 2 | 1 |

^a At a total daily dose of 50 mg, patients should take 1 x 20-mg tablet in the morning and 2 x 15-mg tablets in the evening.

BSA=body surface area (calculate to 2 decimal places)

5.4.2 Non-Hematologic Toxicity

Refer to Table 3 located in this sub-section.

These toxicities can be AEs or laboratory abnormalities such as hepatobiliary or renal laboratory findings.

| Grade ^a | Dose Hold/Resumption within a 28-day Treatment Cycle | Dose Adjustment for Next Cycle |
|--------------------------------|--|-----------------------------------|
| Grade 1 or 2 | | |
| Any occurrence | Maintain treatment at the | None |
| | same dose level | |
| Clinically concerning or treat | tment-related Grade 3 ^b or high | er |
| 1st, 2nd, or 3rd | Suspend treatment until | Reduce by 1 dose level from |
| occurrence | Grade 0 or 1 | the previous level |
| | | |
| 4th occurrence | Discontinue treatment | Discontinue treatment |

Table 3: TAS-102 Dose Modification Schedule for Non-hematologic Toxicities

a Note: For toxicities (AEs or laboratory abnormalities) considered unlikely to become serious or life-threatening (including, but not limited to, fatigue, alopecia, changes in libido, and dry skin), subjects may continue on study medication at the same dose without reduction or interruption at the discretion of the Investigator (irrespective of grade).

b Except for Grade 3 nausea and/or vomiting controlled by aggressive antiemetic therapy or diarrhea responsive to antidiarrheal medication. If there is any uncertainty about continuing study medication or resuming study medication in a subject with Grade \geq 3 non-hematologic toxicities, the case must be discussed with the UFHCC Data and Safety Integrity Committee (DISC) prior to continuing treatment.

5.4.3 Hematologic Toxicity

Obtain complete blood cell counts prior to and on Day 15 of each cycle.

Do not initiate the cycle of LONSURF[®] until:

- Absolute neutrophil count (ANC) is greater than or equal to 1,500/mm³ or febrile neutropenia is resolved
- Platelets are greater than or equal to 75,000/mm³
- Grade 3 or 4 non-hematological adverse reactions are resolved to Grade 0 or 1

Within a treatment cycle, withhold LONSURF[®] for any of the following:

- Absolute neutrophil count (ANC) less than 500/mm³ or febrile neutropenia
- Platelets less than 50,000/mm³
- Grade 3 or 4 non-hematological adverse reactions

After recovery, resume LONSURF[®] after reducing the dose by 5 mg/m²/dose from the previous dose level, if the following occur:

- Febrile neutropenia
- Uncomplicated Grade 4 neutropenia (which has recovered to greater than or equal to 1,500/mm³) or thrombocytopenia (which has recovered to greater than or equal to 75,000/mm³) that results in more than 1-week delay in start of next cycle

• Non-hematologic Grade 3 or Grade 4 adverse reaction except for Grade 3 nausea and/or vomiting controlled by antiemetic therapy or Grade 3 diarrhea responsive to antidiarrheal medication

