6.2 Study Treatment Discontinuation

Study treatment will be withheld under the following circumstances::

- Grade 4 neutropenia (ANC less than 500/mm³ or febrile neutropenia), until ANC is resolved to greater than 1500/mm³ or febrile neutropenia is resolved
- Grade 4 thrombocytopenia or grade 3 thrombocytopenia with bleeding (platelets less than 50,000/mm³), until platelet count resolved to greater than or equal to 75,000/mm³
- Other grade 3 or 4 non-hematologic toxicity, until the adverse reaction has resolved to Grade 0 or 1

A subject will be discontinued from protocol therapy under the following circumstances:

- Any adverse event which, in the Investigator's opinion, requires termination of the study medication.
- Disease progression, unless at the discretion of the Principal Investigator (in collaboration with any co-sponsors or collaborators) determines continued treatment with study drug is appropriate.
- Substantial non-compliance (>25% of missed doses with the exception of dose delays and dose modifications per protocol, or dose-related instructions from research team staff due to adverse events), with the requirements of the study.
- The subject presents with a beta-HCG test consistent with pregnancy and is confirmed to be pregnant. Pregnancy will be reported along the same timelines as a serious adverse event.
- The subject uses illicit drugs or other substances that may, in the opinion of the Investigator, have a reasonable chance of contributing to toxicity or otherwise interfering with the study or its results.

- The development of a second malignancy that requires treatment, which would interfere with this study.
- The subject is lost to follow-up.
- Development of an intercurrent illness or situation which would, in the judgment of the investigator, affect assessments of clinical status and study endpoints to a significant degree.

The Investigator will make every reasonable effort to keep each subject in the study unless it is in the subject's best interests to discontinue participation. If a subject is removed from the study or declines further participation, all End of Treatment evaluations should be performed if the subject is willing and able to be assessed. A description of the reason(s) for withdrawal from the study must be recorded on the case report form (CRF). The Investigator should also ensure that all subjects are followed up for survival status and progression (as applicable) after the End of Treatment Visit.

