7 STUDY PROCEDURES

7.1 Study Schedule of Events

See Table 4 located in this section.

| | | Treatment Ph | ase ^l (1 cycle = 1 | 28 days) | End of | |
|--|---|---|--|--|--|--|
| Evaluation | Screening ^a | Before each cycle (within 3 days) | D15 of each cycle (± 3 days) | Odd # cycles (± 7 days) | treatment (within 30 days post last dose) | Follow Up |
| History & Physical | X | X | | | Х | X ⁱ |
| Performance Status | X | X | | | Х | |
| Vital Signs ^b | X | X | | | Х | |
| AE Assessment | X | X | | | Х | Xj |
| Concomitant Meds | X | X | | | Х | X^k |
| ECG ^c | X | | | | | |
| Pregnancy test ^d | X | | | | | |
| Urine analysis | X | | | | | |
| CMP ^{e,f} | X | X | | | X | |
| Magnesium | X | X | | | Х | |
| CBC w/Diff ^e | X | X | X ^m | | X | |
| PT/INR ^g | X | | | | | |
| CA19-9 | X | Х | | | | |
| CT or MRI ^h | Х | | | Х | | Х |
| Survival Status | | | | | | Х |
| a. All screening procedures s completed within 7 days o required to be repeated at b. Vital signs include height, scale). Height should be o c. ECGs will be obtained at s performed at regular inter d. Pregnancy testing will be pregnancy testing will be physical signs, or sympton | should be completed of treatment. Histor treatment initiation weight, blood pres obtained at screenin screening. Subjects vals (interval timing done for all females conducted any time ms of pregnancy. | d within 28 days of t y & Physical, Vital 3 if they were comple sure, pulse, tempera g only. who are placed on 6 g is at the discretion s of childbearing age clinical signs presen | reatment except for s Signs, ECOG PS, CM ted within 7 days pri ture and pain level (s QT prolonging media of the treating invest at Screening prior to th for potential pregn | serum pregn. I P, CBC w 1 or to Cycle ubjective 1- cations while igator). o TAS-102 i ant state, e.g | ancy testing wh Diff and CA19- 1 Day 1. 10 self-reported e on study shou nitiation. Stand | ich should be 9 are not 1 ld have ECGs lard-of-care other |

Table 4: Study Schedule and Procedures

Laboratory testing may be performed up to 72 hours prior to day 1 of the next cycle of therapy.

CMP: Na, K, Cl, CO₂, Glucose, BUN, Creatinine, Ca, Albumin, Total Bilirubin, Alk Phos, Total Protein, AST, ALT.

PT/INR should be followed closely for subjects on warfarin.

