9 STUDY DRUG INFORMATION

- 9.1 Study Drug Name TAS-102 (Lonsurf[®])
 - 9.1.1 Drug Supply TAIHO Oncology, Inc.
 - 9.1.2 Contraindications: none
 - 9.1.3 Special Warnings and Precautions for Use

Myelosuppression

In Study 1, LONSURF[®] caused severe and life-threatening myelosuppression (Grade 3-4) consisting of anemia (18%), neutropenia (38%), thrombocytopenia (5%) and febrile neutropenia (3.8%). One patient (0.2%) died due to neutropenic infection. In Study 1, 9.4% of LONSURF[®]-treated patients received granulocyte-colony stimulating factors.

Obtain complete blood counts prior to and on Day 15 of each cycle of LONSURF[®] and more frequently as clinically indicated. Withhold LONSURF[®] for febrile neutropenia, Grade 4 neutropenia, or platelets less than 50,000/mm³. Upon recovery, resume LONSURF[®] at a reduced dose.

Embryo-Fetal Toxicity

Based on animal studies and its mechanism of action, LONSURF[®] can cause fetal harm when administered to a pregnant woman. Trifluridine/tipiracil caused embryo-fetal lethality and embryo-fetal toxicity in pregnant rats when orally administered during gestation at dose levels resulting in exposures lower than those achieved at the recommended dose of 35 mg/m² twice daily.

Advise pregnant women of the potential risk to the fetus. Advise females of reproductive potential to use effective contraception during treatment with LONSURF[®].

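### After febrile neutropenia, 5.4.3 and 6.2 let dosing start or resume with no ANC floor, while 5.1 conditions continued cycles on an ANC of at least 1,500/mm³

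*Combined protocol and SAP*

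**What the plan says.** Three places in the protocol set the neutrophil condition for giving more drug.

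- **5.1 Treatment Schedule/Administration.** Cycles continue every 28 days in the absence of significant treatment-related abnormalities and on "documentation of an ANC greater than or equal to 1500/ mm³ and platelet count of greater than or equal to 75,000/ mm³". There is no alternative route for febrile neutropenia.
- **5.4.3 Hematologic Toxicity.** The list of conditions that bar a new cycle has as its neutrophil line "Absolute neutrophil count (ANC) is greater than or equal to 1,500/mm³ or febrile neutropenia is resolved". Separate lines cover platelets and non-hematologic toxicity.
- **6.2 Study Treatment Discontinuation.** A hold for Grade 4 neutropenia, a term under which 6.2 places both ANC below 500/mm³ and febrile neutropenia, lasts "until ANC is resolved to greater than 1500/mm³ or febrile neutropenia is resolved".

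5.4.3 also has a list for resuming at a reduced dose after recovery. Uncomplicated Grade 4 neutropenia carries a recovery value of at least 1,500/mm³ there. The febrile neutropenia item carries none. Section 9.1.3 says "Withhold LONSURF[®] for febrile neutropenia, Grade 4 neutropenia, or platelets less than 50,000/mm³" and then to resume at a reduced dose on recovery, again without an ANC value.

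**The concern.** The ANC level and the resolution of febrile neutropenia are joined by 'or' in 5.4.3 and 6.2, so the second can stand in for the first. 5.1 does not allow that substitution, and the protocol does not say which section prevails.

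The subject concerned has just had febrile neutropenia and is about to receive more of a myelosuppressive drug. Section 9.1.3 reports Grade 3-4 neutropenia in 38% of Study 1 patients and one death from neutropenic infection. A site that works from the start list in 5.4.3, the natural place to look on a hematologic question, could begin a cycle below the level that 5.1 sets. What is at stake is subject safety and uniform dosing across sites.

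**Working it through.** No figure in the plan depends on this rule, so the check is a comparison of the rules followed by a rough size.

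**1. The rules applied to the same subject.** Assume platelets of at least 75,000/mm³ and no unresolved Grade 3-4 non-hematologic toxicity, so that only the neutrophil condition decides.

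| State at the decision | 5.1, continue cycles | 5.4.3, start list | 6.2, end of hold |
|---|---|---|---|
| Febrile neutropenia resolved, ANC below 1,500 | not met | met | met |
| Febrile neutropenia resolved, ANC above 1,500 | met | met | met |
| Grade 4 neutropenia without fever, ANC below 1,500 | not met | not met | not met |
| Grade 4 neutropenia without fever, ANC exactly 1,500 | met | met | not met |

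The first row is the conflict. The last row is a small separate slip: 6.2 asks for more than 1,500, the other sections for at least 1,500.

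**2. Within a cycle.** 5.1's ANC condition concerns continuation from cycle to cycle. It does not govern release of a hold inside a cycle. There the operative texts are 6.2 and the resumption list in 5.4.3, and for febrile neutropenia neither gives an ANC level. The window is short: 5.1 has "the last dose administered in the evening of Day 12", and held doses are not made up. The scheduled mid-cycle count in Table 4 is Day 15 ± 3, so the earliest is Day 12 (15 − 3 = 12). A release before then would rest on an unscheduled count.

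**3. Size.** Inputs: 37 subjects to be accrued (12.1), or 33 (Synopsis and 3.1); febrile neutropenia 3.8% in Study 1 (9.1.3), with 533 treated patients (9.1.4). Assumption: the colorectal rate carries over to pancreatic cancer.

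- 37 × 0.038 = 1.41 subjects with febrile neutropenia; 33 × 0.038 = 1.25.
- Sampling error of the borrowed rate: 0.038 × 533 ≈ 20 patients. The exact (Clopper-Pearson) 95% limits for 20/533 are 2.31% and 5.74%, so 37 × 0.0231 = 0.85 and 37 × 0.0574 = 2.12.

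These count the parent event. The conflict also needs febrile neutropenia to have resolved with ANC still below 1,500 at the time of the decision. The documents give no fraction for that; it may be zero.

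**The case against.** **5.1 is the default and 5.4.3 the exception.** 5.1 opens with the absence of significant treatment-related abnormalities, and febrile neutropenia is one, so 5.1 may not be meant for this subject. If so, the conflict between sections goes, but the subject is left with no ANC floor anywhere. The gap stands.

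**The 'or' is meant respectively:** ANC recovery for Grade 4 neutropenia, resolution for febrile neutropenia. This is a natural reading. It leaves the subject after febrile neutropenia with an undefined word in place of a level, which is the same gap.

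**The sections can be obeyed together.** This stands. A reader might infer that 5.1 and 5.4.3 are irreconcilable, or that 5.1 says cycles continue only at 1,500. The documents do not support either. The word 'only' is not in 5.1, and 5.4.3 is a prohibition, so a site that applies every section simply waits for 1,500 before the next cycle. The problem at cycle start is one of clarity.

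**The risk is already reduced.** This also stands. 5.4.3 requires a reduction of 5 mg/m² per dose after febrile neutropenia, 5.3.1 permits G-CSF, and a count is taken before every cycle.

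**Platelets.** A reader might infer from the trigger in 6.2, "Grade 4 thrombocytopenia or grade 3 thrombocytopenia with bleeding (platelets less than 50,000/mm³", that non-bleeding Grade 3 thrombocytopenia needs no hold. The documents do not support that. 6.2 does not claim to list every reason to withhold, its own parenthesis gives the same number, and both 5.4.3 ("Platelets less than 50,000/mm³") and 9.1.3 require a hold below 50,000/mm³ whether or not there is bleeding.

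**Conclusion.** The point holds as a minor safety wording correction. Read literally, 5.4.3 and 6.2 allow a cycle to start, or a hold to end, below the ANC level that 5.1 sets, in subjects whose febrile neutropenia has resolved. For a resumption within a cycle, no section supplies a floor. This rests on the current text alone.

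Few subjects are likely to be affected: about 1.4 of 37 (0.9 to 2.1) with febrile neutropenia if the Study 1 rate carries over, and an unknown fraction of those in the conflicting state. It is tempting to treat these figures as upper bounds. They are not, because the rate comes from another disease and the limits reflect only sampling error in that population.

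Sample size, power, alpha and the PFS analysis do not depend on the rule.

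**What to change.** In the start list of 5.4.3 and the end-of-hold rule of 6.2, replace the neutrophil condition with: *ANC greater than or equal to 1,500/mm³ and, if febrile neutropenia occurred, its resolution*. This agrees with 5.1, gives a floor for resumption within a cycle, and removes the mismatch between more than and at least 1,500 in 6.2. The febrile neutropenia item in the resumption list of 5.4.3 can refer to the same condition.

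Rewording the platelet trigger in 6.2 as any count below 50,000/mm³ is an optional tidy-up in the same amendment.

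The cost is a few words in two sections, with no new visits, tests or subjects. The downside is an occasional short hold or cycle delay. A subject held within a cycle may lose the remaining doses up to Day 12, since held doses are not made up.
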